Efficacy Evaluation	Efficacy evaluation indicators (primary and secondary efficacy indicators)Primary outcome indicator: Time for dynamic lung compliance (C_{dyn}) to return to baseline after lung recruitment;Secondary outcome indicators: Degree of atelectasis immediately after extubation, evaluated by lung ultrasound; oxygenation index at T0-T5; incidence of hypoxemia and duration of oxygen therapy during PACU stay; pulmonary complications within 3 days after surgery, evaluated by postoperative chest X-ray or CT, with atelectasis assessed by lung ultrasound.
	Safety evaluation indicators: None
Statistical Methods	Descriptive statistics, Mann-Whitney U test, t-test, Chi-square test, etc.

2. Research Background

During perioperative mechanical ventilation, high fractional inspired oxygen (FiO_2) is usually administered to prevent hypoxemia. Although numerous studies have shown that the use of high FiO_2 during surgery can improve oxygen supply to vital organs such as the heart, brain, and kidneys, inhalation of high-concentration oxygen is also a risk factor for postoperative pulmonary complications. Therefore, there is no consensus on the optimal intraoperative FiO_2 setting[1].

Lung recruitment typically includes manual lung recruitment and ventilator-driven lung recruitment, with the latter including vital capacity maneuver, pressure-controlled method, and volume-controlled method. Various lung recruitment methods can effectively open alveoli and improve oxygenation[3].

Evaluation of lung recruitment efficacy includes pressure-volume (P-V) curve, electrical impedance tomography (EIT), and lung ultrasound (LUS).

The P-V curve describes the relationship between airway pressure and tidal volume, reflecting the mechanical properties of the lungs and chest wall, and can assist in judging the

ventilation status of the lungs. A normal P-V curve is "S"-shaped, with the zero point representing functional residual capacity (FRC), and the volume change range being tidal volume. The P-V curve is an effective bedside tool for evaluating respiratory mechanics and lung recruitment efficacy.

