6.7 Study-Related Imaging Examinations

Electrocardiogram

7. Efficacy Evaluation Criteria

Observation of primary outcome indicators: Time for dynamic lung compliance (Cdyn) to return to baseline after lung recruitment. Respiratory mechanics parameters and hemodynamic parameters at T1-T5 were recorded, including Cdyn, PIP, Ppeak, Pplat, Vt, PEEP, MP, Pdrive, BP, HR;

Observation of secondary outcome indicators: Degree of atelectasis immediately after extubation, evaluated by lung ultrasound; oxygenation index at T0-T5; incidence of hypoxemia and duration of oxygen therapy during PACU stay; pulmonary complications within 3 days after surgery, evaluated by postoperative chest X-ray or CT, with atelectasis assessed by lung ultrasound.

8. Observation Items and Detection Time Points

Before the first lung recruitment (RM1) after surgery starts (T1), immediately after RM1 (T2), before RM2 (T3), immediately after RM2 (T4), and immediately at the end of surgery (T5). Primary and secondary outcome indicators were observed. Degree of atelectasis immediately after extubation, evaluated by lung ultrasound; oxygenation index at T0-T5; incidence of hypoxemia and duration of oxygen therapy during PACU stay; pulmonary complications within 3 days after surgery, evaluated by postoperative chest X-ray or CT, with atelectasis assessed by lung ultrasound.

9. Observation of Adverse Events

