12.1 Statistical Methods

All data were statistically analyzed using SPSS 26.0 software, with $P<0.05$ indicating a statistically significant difference. Count data were expressed as cases or percentages and analyzed using the Chi-square test or Fisher's exact test. Normality of measurement data was evaluated using the Kolmogorov-Smirnov test or Shapiro-Wilk test. Measurement data conforming to a normal distribution were expressed as mean \pm standard deviation ($x\pm s$) and analyzed using the t-test; count data with repeated measurements were analyzed using one-way ANOVA; skewed or unknown-distribution measurement data were expressed as median (interquartile range) [median (IQR)] and analyzed using the Mann-Whitney U test.

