12.2 Sample Size Calculation Process

88 cases
Sample size calculation process Based on preliminary experimental results, sample size was calculated using PASS, with a 20% dropout rate, resulting in a total sample size of 88 cases (22 cases in each group).

Input:

Power and Alpha

Power 0.95

Alpha 0.05

Group 4

Group Allocation Equal

Effect size

Means 30 34 50 53

K 1

σ 761519

Numeric Results
Means: 30 34 50 53

Power	Average	n	G	Total	K	Std Dev of Means	Standard Deviation	Effect Size	Alpha
0.9707	3.00	4		12	1.00	9.91	6.00	1.6515	0.0500
0.9875	4.00	4		16	1.00	9.91	7.00	1.4156	0.0500
0.9526	11.00	4		44	1.00	9.91	15.00	0.6606	0.0500
0.9526	17.00	4		68	1.00	9.91	19.00	0.5215	0.0500

One-Way Analysis of Variance F-Tests

Dropout-Inflated Sample Size (Continued)

Average Group Sample Size n	Group	Dropout Rate	Sample Size	Dropout-Inflated Enrollment Sample Size Ni	Expected Number of Dropouts Di
17.00	1 - 4	20%		17	22
	Total		68	88	5

13. Ethics of Clinical Research

The clinical study will follow the World Medical Association Declaration of Helsinki and other relevant regulations. Before the start of the study, the trial protocol will be implemented only after approval by the ethics committee. Before each subject is enrolled in the study, the investigator is responsible for fully and comprehensively introducing the purpose, procedures, and possible risks of the study to the subject or their agent, and a written informed consent form will be signed. Subjects should be informed that they have the right to withdraw from the study at any time. The informed consent form should be retained as a clinical study document for reference. The privacy and data confidentiality of subjects will be protected during the study.

14. Collection and Storage of Samples/Specimens

None.

15. Study Progress

Not available.

16. References

[2] Neira VM, Kovesi T, Guerra L, Campos M, Barrowman N, Splinter WM. The impact of pneumoperitoneum and Trendelenburg positioning on respiratory system mechanics during

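### Section 12.1 lets a normality pretest on the trial's own data choose between a t-test and a rank test for the primary outcome, so the primary hypothesis and summary depend on the data even though the branching is written in advance

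*Protocol*

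**What the plan says.** The primary outcome is given in section 7: "Observation of primary outcome indicators: Time for dynamic lung compliance (Cdyn) to return to baseline after lung recruitment". It is a continuous time, so it counts as measurement data.

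Section 12.1 opens with a general scope, "All data were statistically analyzed using SPSS 26.0 software", and gives no separate rule for the primary outcome. The rule for measurement data has three parts:

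- Pretest: "Normality of measurement data was evaluated using the Kolmogorov-Smirnov test or Shapiro-Wilk test".
- First branch: "Measurement data conforming to a normal distribution were expressed as mean" and SD, compared by t-test.
- Second branch: "skewed or unknown-distribution measurement data were expressed as median (interquartile range"), compared by Mann-Whitney U.

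The Statistical Methods row of the Protocol Summary repeats the menu without naming a primary test: "Descriptive statistics, Mann-Whitney U test, t-test, Chi-square test, etc".

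The sample size in section 12.2 rests on "One-Way Analysis of Variance F-Tests" for four groups. Section 12.1 uses ANOVA only here: "count data with repeated measurements were analyzed using one-way ANOVA". The sizing section therefore does not settle which test is primary.

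**The concern.** A t-test compares means. A Mann-Whitney test compares ranks, and when the groups differ in spread or shape it can reject although the means are equal. The choice of branch therefore changes the question answered as well as the efficiency of the answer. Here the branch is set by a preliminary test on the same data, at a sample size (17 evaluable, 22 enrolled per arm) where such a test has limited power to detect skewness and also rejects truly normal data by chance.

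At stake is whether the primary hypothesis and the reported summary are fixed before the data are seen. The planning SDs range from 6 to 19, so the two branches need not address the same null hypothesis.

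**Working it through.** **Inputs.** Planning means 30, 34, 50, 53 and alpha 0.05 (section 12.2 and Protocol Summary); SDs 7, 6, 15, 19 (Protocol Summary), taken in the same group order; 17 evaluable and 22 enrolled per arm. The documents give no distribution shape, so the normal, gamma and log-normal shapes are assumptions.

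**The plan's own figure.** The average mean is 167/4 = 41.75. The SD of means is √[(11.75² + 7.75² + 8.25² + 11.25²)/4] = √(392.75/4) = 9.909. With SD 19, f = 9.909/19 = 0.5215. At n = 17, λ = 68 × 0.5215² = 18.5 with 3 and 64 df, and the noncentral F power is 0.9526, as stated. Inflation for dropout: 17/0.80 = 21.25, rounded up to 22, and 4 × 22 = 88. The sizing reproduces.

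**How often the pretest sends a trial to the rank branch.** Each arm is tested at 0.05 and the rank branch is taken if any of the four arms fails. Kolmogorov-Smirnov uses the Lilliefors correction. There were 2,000 simulated trials per row.

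| n per arm | Shape | Shapiro-Wilk | Kolmogorov-Smirnov | The two disagree |
|---|---|---|---|---|
| 17 | normal | 18% | 19% | 17% |
| 17 | gamma | 36% | 28% | 22% |
| 17 | log-normal | 54% | 40% | 28% |
| 22 | normal | 17% | 17% | 17% |
| 22 | gamma | 43% | 32% | 26% |
| 22 | log-normal | 65% | 48% | 30% |

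The normal rows are what chance gives for four independent tests at 5%: 1 − 0.95⁴ = 18.5%.

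**Rejection rate under equal means.** Two groups, both with mean 42 (the planning average, rounded). The rank test is used if Shapiro-Wilk fails in either group, otherwise the t-test. There were 4,000 runs; the Monte Carlo standard error is √(0.05 × 0.95/4000) = 0.0034.

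| Shape, SDs | n | Fixed t-test | Fixed Mann-Whitney | Two-stage rule |
|---|---|---|---|---|
| normal, 19 and 19 | 17 | 0.051 | 0.054 | 0.054 |
| normal, 19 and 19 | 22 | 0.054 | 0.050 | 0.054 |
| log-normal, 19 and 19 | 17 | 0.049 | 0.052 | 0.058 |
| log-normal, 19 and 19 | 22 | 0.053 | 0.053 | 0.059 |
| normal, 7 and 19 | 17 | 0.058 | 0.065 | 0.062 |
| normal, 7 and 19 | 22 | 0.056 | 0.065 | 0.059 |
| log-normal, 7 and 19 | 17 | 0.067 | 0.109 | 0.108 |
| log-normal, 7 and 19 | 22 | 0.069 | 0.136 | 0.126 |

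The last two rows stand out because equal means no longer imply equal medians. A log-normal median is mean/√(1 + (SD/mean)²). With SD 7 this is 42/√1.0278 = 41.4; with SD 19 it is 42/√1.2047 = 38.3. The rank test responds to that difference, which is not a difference in means.

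**Effect on the overall verdict at the planning values.** With 17 per arm and 1,500 simulated trials per shape, one-way ANOVA and Kruskal-Wallis gave different verdicts in 0.2% of normal and 0.0% of log-normal trials.

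**The case against.** The strongest reply is that section 12.1 does fix its rule in advance: each outcome of the pretest has a named test and a named summary. That stands. A reader might infer that the analyst may pick whichever test looks better once results are known, but the text does not grant that. Which normality test is used, at what level and on what unit may also be set out in an analysis plan that is not shown, so those gaps are not counted here. What remains is the switch itself, which the protocol states.

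Three stronger readings are tempting and should not be drawn.

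- *The pretest will almost always reject.* Run on all arms pooled, Shapiro-Wilk rejects in about 93% of trials even when every arm is normal, because the arms differ in spread. The protocol nowhere says the arms are pooled, and the t-test's assumption concerns distributions within groups. The arm-by-arm figures are the fair ones.
- *The pretest flips the conclusion in about one trial in eleven.* For log-normal data, the t-test and Mann-Whitney disagree on the 30 v 34 contrast in 9% of trials. That figure does not depend on the pretest and is the worst of six contrasts; the others range from 0.0% to 2.8%. Disagreement between the pretests together with disagreement on that contrast occurs in about 2.5%.
- *The type I error is broadly inflated.* It is not. Under equal means the rule rejects in 5% to 6% except in the one unequal-SD, log-normal setting, whose shape is assumed.

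The protocol also names summary measures only. That the between-group effect measure changes with the branch is an inference, though a natural one.

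**Conclusion.** The point holds as a modest specification defect that should be corrected. The primary hypothesis and summary depend on a normality test of the trial's own data. With 17 per arm, that test takes the rank branch in about 18% of trials for purely chance reasons when data are normal, and in about 40% to 55% if times are log-normal, where the two permitted pretests disagree in about 28%.

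The harm is mainly that the estimand is not fixed. Error rates matter in one setting: SDs of 7 and 19 with log-normal times, where rejection under equal means is about 11% at 17 per arm and 13% at 22, against about 7% for a fixed t-test. At the planning effect the four-group conclusion is practically unaffected. These sizes rest on the planning means and SDs, arm-by-arm testing at 0.05 and the assumed shapes.

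**What to change.** In section 12.1, remove the normality pretest as the selector for the primary outcome and state in advance:

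1. One primary test comparing all four groups, consistent with the one-way ANOVA used for sizing. A version robust to unequal variances (Welch) is acceptable given the planned SDs. In 1,500 simulated trials with normal data, the planning means and each arm's own SD, power at 17 per arm was 0.999 for the standard F-test and 1.000 for Welch.
2. One effect measure: difference in means with 95% CI.
3. Kruskal-Wallis as a sensitivity analysis, run whatever the normality result, with residuals inspected descriptively only.

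The test must span all four groups. Naming the t-test alone would remove the switch but leave six pairwise comparisons; unadjusted, these give a family-wise error of about 0.20 by simulation under a common null.

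The Statistical Methods row of the Protocol Summary should be brought into line. The cost is a few sentences. If the sizing ANOVA is named, N stays at 68 evaluable and 88 enrolled. The only loss is the freedom to switch tests.

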6.5 Study Flowchart

![img](Patients enter the operating room

Preoxygenation followed by tracheal intubation

Adjust to group-specific FiO₂ after surgery starts

Group A: FiO₂ 30%

Group B: FiO₂ 40%

Group C: FiO₂ 60%

Group D: FiO₂ 80%

First lung recruitment after 10 minutes

Record the duration of improved lung compliance

Next lung recruitment after compliance returns to baseline, and so on

All patients undergo lung recruitment immediately at the end of surgery,

Transfer to PACU, record incidence of hypoxemia and duration of oxygen therapy)

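### Section 12.1 gives one-way ANOVA to repeated count data; the outcomes clearly listed at serial times are continuous, and one-way ANOVA does not account for repeated readings from one patient

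*Protocol*

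**What the plan says.** Section 12.1 sorts the data by type and gives each type a test:

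- Count data: "Count data were expressed as cases or percentages and analyzed using the Chi-square test or Fisher's exact test".
- Normally distributed measurement data: summarised as mean and standard deviation and compared with the t-test.
- Skewed measurement data: the Mann-Whitney U test.
- Repeated data: "count data with repeated measurements were analyzed using one-way ANOVA".

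The serial outcomes are in Sections 7 and 8. Section 7 states: "Respiratory mechanics parameters and hemodynamic parameters at T1-T5 were recorded, including Cdyn, PIP, Ppeak, Pplat, Vt, PEEP, MP, Pdrive, BP, HR". Both sections also list "oxygenation index at T0-T5". Section 8 places T1 and T2 just before and just after the first recruitment, T3 and T4 just before and just after the second, and T5 at the end of surgery.

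The statistical row of the Protocol Summary reads: "Descriptive statistics, Mann-Whitney U test, t-test, Chi-square test, etc". No repeated-measures ANOVA, mixed model, GEE or Friedman test is named anywhere in the protocol.

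**The concern.** The clause fails in two ways.

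**Data type.** ANOVA is not a method for counts, and the paragraph has already given counts another test. Hypoxemia in the PACU and pulmonary complications within 3 days are listed as incidences, without serial time points. The series that are listed are continuous. *Count* is probably a slip for *measurement*, but that is an inference.

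**Structure.** Correcting the word does not repair the clause. One-way ANOVA assumes independent observations, and up to six readings from one patient are not independent.

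At stake is the validity of the tests on oxygenation index, a named secondary outcome, and on the supporting respiratory and hemodynamic parameters. The clause can be applied in several ways with very different error rates, so the choice could be made after the data are seen.

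**Working it through.** **1. The plan's own figure, to see whether this clause touches it.** Section 12.2 sizes the trial on a between-group one-way ANOVA.

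- The assumed means 30, 34, 50 and 53 average 41.75. The squared deviations sum to 138.06 + 60.06 + 68.06 + 126.56 = 392.75, so the SD of the means is √(392.75/4) = 9.91, as stated.
- With 17 per group and SD 19, the noncentrality is 68 × (9.909/19)² = 18.5. With 3 and 64 degrees of freedom the power is 0.9526, as stated.
- Dropout: 17/(1 − 0.20) = 21.25, rounded up to 22 per group, or 88 in total.

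The figure reproduces. It uses one value per patient, so the repeated-data clause does not affect it.

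**2. Matching outcomes to methods.**

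| Outcome | Type | Occasions | Method in 12.1 |
|---|---|---|---|
| Oxygenation index | continuous | T0-T5 | none that fits |
| Cdyn, pressures, Vt, PEEP, MP, BP, HR | continuous | T1-T5 | none that fits |
| PACU hypoxemia | count | one incidence per patient | Chi-square/Fisher |
| 3-day pulmonary complications | count | one incidence per patient | Chi-square/Fisher |

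**3. What each application of the clause would do.** The protocol gives no within-patient correlation, so these are assumed: constant at 0.3, 0.5 or 0.7, or AR(1) at 0.5, 0.7 or 0.9. Setting: 4 arms × 22 patients, five times (T1-T5), normal outcome, complete data, no true effect, nominal 5%, 20,000 simulated trials per setting.

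| Application | Constant 0.3 / 0.5 / 0.7 | AR(1) 0.5 / 0.7 / 0.9 |
|---|---|---|
| Groups compared at each time, per test | about 5% | about 5% |
| Same, at least one false positive in five | 12-22% over all settings | 12-22% over all settings |
| Times compared, patient ignored | at most about 2% | at most about 2% |
| Repeated-measures ANOVA, uncorrected: time | about 5% (sphericity holds) | 6.4 / 7.0 / 7.9% |
| Repeated-measures ANOVA, uncorrected: group x time | about 5% (sphericity holds) | 6.4 / 7.9 / 9.2% |
| Readings pooled across arms as independent | 31 / 47 / 57% | 33 / 47 / 61% |

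Repeat runs move these by about one point, hence the rounded ranges of 6-10% for group x time and 30-60% for pooling.

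Two checks by hand:

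- Five independent tests would give 1 − 0.95⁵ = 22.6% for at least one false positive. Correlation between times lowers this, which agrees with 12-22%.
- Pooling five readings at constant correlation ρ inflates the between-group mean square by about 1 + 4ρ, that is 2.2, 3.0 and 3.8. The 5% critical value of F(3, 436) is about 2.63. Dividing it by these factors and referring the result to F(3, 84) gives about 32%, 46% and 56%, close to the simulation.

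**4. Does the proposed replacement hold its level?** With complete data, multivariate tests that use an unstructured covariance (Hotelling for time, Pillai for group x time) reject 4.7-5.4% of null trials (10,000 per setting; constant 0.5, the three AR(1) settings, and one structure tying T1 to T3 and T2 to T4).

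**5. Patients without T3 and T4.** RM2 follows the return of compliance to baseline (Sections 4.2 and 6.3). A patient whose compliance has not returned before surgery ends has no T3 or T4. As an illustration, assume return times in minutes, normally distributed, with the listed mean 53 paired with SD 19. Assume also a 90-minute operation with the first recruitment 10 minutes in, which leaves 80 minutes. Then (80 − 53)/19 = 1.42, and about 8% of that arm would lack these readings. Standard repeated-measures ANOVA drops such patients; a mixed model uses the readings they have.

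**The case against.** **The clause may be loose wording.** It may mean repeated-measures ANOVA, or a comparison of the four groups at each time. On those readings the error is modest, and a sphericity correction is the sort of detail an SAP settles. This stands as a limit on the size of the problem. It does not rescue the clause, because the protocol is not silent: it names a specific procedure, and Section 12.2 uses the same procedure in its ordinary between-group sense.

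**A reader might infer a false-positive rate of up to 60%.** The document does not support that. The rate requires pooling each patient's readings as independent, which no section states, and the correlations are assumed.

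**A reader might infer that the primary outcome is affected**, since Section 7 lists the T1-T5 parameters, including Cdyn, beside it. The primary outcome is the time for Cdyn to return to baseline, not the Cdyn series. Nor does the flowchart line "Next lung recruitment after compliance returns to baseline, and so on" show that return times from later recruitments will be analysed.

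**A reader might say that no count outcome is repeated.** That is too absolute. Section 3.2 gives an incidence of atelectasis after extubation, and Sections 7 and 8 mention atelectasis by ultrasound again with the 3-day complications. The text does not settle whether this is one categorical outcome assessed twice. One-way ANOVA would not suit it either.

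**The Protocol Summary is weak evidence.** Its list is open-ended and also omits the ANOVA and Fisher tests that Section 12.1 names.

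**Conclusion.** The clause is wrong as written, in data type and in structure, and should be corrected. What is shown is an ambiguity with a range of consequences, not one error rate: about 5% per test with 12-22% over five times, well below 5% if times are compared ignoring the patient, about 6-10% for group x time with uncorrected repeated-measures ANOVA under AR(1), and 30-60% only under a pooling that the protocol does not describe. These figures rest on assumed correlations, normal outcomes, complete data and five times; the sixth reading of oxygenation index (T0) was not simulated. The effect is confined to oxygenation index and the supporting parameters. The primary time-to-return outcome and the sample size of 88 are untouched by this clause.

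**What to change.** In Section 12.1, replace the clause with: *Continuous outcomes measured repeatedly are analysed with a linear mixed model with group, time and group x time and an unstructured within-patient covariance.* Keep Chi-square or Fisher's exact test for count outcomes recorded on a single occasion.

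Naming one method is better than offering a choice between a mixed model and repeated-measures ANOVA, which would leave the analysis open. The mixed model also keeps patients who lack T3 and T4 because RM2 was not reached, on the usual assumption that their observed readings account for the gap.

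Add a note that Cdyn at T3 is to be interpreted with care. RM2 is triggered by return to baseline, so T3 lies near baseline by design in every arm, and T3 and T4 fall at different clock times if return times differ between arms.

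The cost is one sentence, one note and slightly more analysis work. SPSS 26.0, already named, fits the model, and no further data need to be collected.
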